10.3. Withdrawal of Participants From Study

Participants must be withdrawn from the study for any one of the following reasons:

- The participant withdraws consent.
- The participant enrolls into another interventional clinical study in which an investigational treatment or approved therapy for investigational use is administered.
- The participant is unwilling or unable to comply with the protocol.

The primary reason for the participant's withdrawal from the study must be recorded in the participant's CRF.

Participants who withdraw from the study prematurely are to return to the study site for an Early Termination (ET) Visit and assessments as indicated in [Table 1](#), after the reason for withdrawal is identified. For such participants, clinical efficacy assessments specified at the ET Visit are not required if the participant discontinues treatment within 3 months of the previous primary efficacy (CDR) assessment and no significant changes in cognitive status are suspected by the Investigator; the study site should notify the Sponsor in such cases. An MRI scan should be performed if withdrawal occurs ≥ 6 months after the previous MRI. Blood for biomarker analysis should be collected if the participant withdraws ≥ 4 weeks after the previous sample was collected.

CONFIDENTIAL

The information contained herein may not be used, disclosed, or published without the written consent of Biogen MA Inc.

Participants who are withdrawn from the study are also to return to the study site for a Follow-up Safety Visit 14 weeks after receiving the last dose of study treatment.

[REDACTED]

[REDACTED]

CONFIDENTIAL

The information contained herein may not be used, disclosed, or published without the written consent of Biogen MA Inc.

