The frequency of MRIs was adjusted by removing MRI from Week 176 and Week 128 and adding it to Week 156. MRI will now be performed at Week 104 (6 months after start of LTE), Week 156 (18 months after start of LTE), and Week 226 (36 months after start of LTE). A row for body weight was added to Tables 2 through 4. Body weight measurements were added to all clinical visits that include a physical examination. A row for tobacco use status was added to Tables 1 through 4 below concomitant therapy and procedures reporting.

Biomarker

The frequency of PK/biomarkers/anti-BIIB092 antibodies collection during the LTE was adjusted for multiple study visits. PK/biomarkers/anti-BIIB092 antibodies will now be assessed at Week 116, Week 156, Week 196, and Week 224.

Clinical Assessments

Removal of NPI-10 and FAQ at Week 176 and ISLT, DKEFS, DSST, Trails A, and eCog at Week 180.

Rationale: To reduce the burden to participants, the original 4 MRIs planned during the LTE at Weeks 104, 128, 176, and 226 (at 6, 12, 24, and 36 months after starting the LTE, respectively) were reduced to 3 MRIs at Weeks 104, 156, and 226 (at 6, 18, and 36 months after starting the LTE, respectively). The Week 104 MRI represents a critical safety assessment for participants switching from placebo to treatment during the LTE. The Week 226 MRI is key for PD evaluation and for safety assessment at the end of the study. The Week 128 and Week 176 MRIs were condensed into a single Week 156 MRI in order to minimize participant burden. Based on

CONFIDENTIAL

The information contained herein may not be used, disclosed, or published without the written consent of Biogen MA Inc.

current evaluations, this frequency of MRI monitoring is not expected to significantly affect the participants' benefit-risk. In addition, ad hoc MRI visits are possible as needed.

The frequency of biomarker and clinical assessments was reduced to decrease the burden to participants, particularly towards the end of the study.

A row for body weight was added to Tables 2 through 4 to provide further clarification on the frequency of body weight measurements.

A row for tobacco use status was added to Tables 1 through 4 to provide clarification on frequency and timing of the assessment.

This change also affects Section 11.4.3, Tobacco Use.

Section 5, Schedule of Activities

Change: A footnote was added to Table 1 for the Week 78 MRI.

Now reads:

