3.1 Analysis Sets

- **Full Analysis Set (FAS):**
The FAS includes all randomized subjects who received at least one dose of study treatment (BIIB092 or placebo). In analyses performed on the FAS, subjects will be analyzed, based on the intention-to-treat principle, according to their randomized treatment assignment regardless of treatment received.
- **Safety Analysis Set:**
The safety Analysis Set includes all randomized subjects who received at least one dose of study treatment (BIIB092 or placebo), essentially the same set of participants included in the FAS. In analyses performed on the Safety Analysis Set, subjects will be analyzed according to their actual treatment received.
- **Safety MRI Evaluable Set:**
The Safety MRI Evaluable Set is defined as subjects in the FAS who had at least one post-baseline safety MRI scan.
- **Serum PK Evaluable Set:**
The serum PK evaluable set is defined as subjects in the FAS who had at least one measurable post-baseline BIIB092 concentration in serum before the End of Study of LTE.
- **CSF PK Evaluable Set:**
The CSF PK evaluable set is defined as subjects in the FAS who had at least one measurable post-baseline BIIB092 concentration in CSF.
- **CSF PD Evaluable Set:**
The CSF PD evaluable set is defined as subjects in the FAS who had lumbar puncture (LP), which will be used in analyses, such as subject accounting and summary of AE related to LP. The CSF PD Modified Evaluable Set is defined as subjects in the FAS who have baseline and at least one post baseline assessment of the specific parameter being analyzed in CSF.
- **Tau PET Evaluable Set**
The tau PET evaluable set is defined as subjects in the FAS who had tau PET, which will be used in analyses, such as subject accounting and summary of AE related to tau PET. The tau PET Modified Evaluable Set is defined as subjects in the FAS who had a valid baseline and a post-baseline tau PET SUVR measure using the 18F-MK6240 tracer.

	Statistical Analysis Plan Long-Term Extension Period	V1.0
---	---	-------------

- Anti-drug antibody (ADA) Evaluable Set:
The evaluable set for anti-drug antibody is defined as subjects in the FAS who have an evaluable post-baseline ADA sample.

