3.2 Analyses Period

Depending on the purpose, different analyses will be conducted on the following study periods:

1. LTE period. Only data in the LTE period will be included in these analyses. This LTE analysis period will be applied to all the AE analyses, and the analyses will include all subjects who were dosed in the LTE period.
2. Placebo-controlled and LTE period. All the data in the placebo-controlled and LTE periods will be included in these analyses. This analysis period will be applied to analyses including, but not limited to all efficacy analyses and listings. The analyses will include all subjects who were dosed in the study including those who did not enroll into the LTE period. For example, line plot of CDR sum of box mean change from baseline over time. in the placebo-controlled and LTE period.
3. Placebo-controlled and LTE active treatment period. Active treatment period is defined as the study period(s) that a subject received BIIB092. For early start subjects – subjects who received BIIB092 in both placebo-controlled and LTE period, all the data (placebo-controlled and LTE periods) will be included in the analyses. For late start subjects – subjects who received placebo in the Placebo-controlled period and BIIB092 in the LTE period, only data in the LTE period will be included. This analysis period will be applied to majority of safety tables, and the analyses will include all subjects who were dosed in the study except for subjects who received only placebo in the placebo-controlled period and did not get dosed in the LTE period. An example is the incidence rate of adverse events in the placebo-controlled and LTE active treatment period.

Subjects to be included in a certain output is determined by both the analysis set and the analysis period. For example, the incidence table of adverse events in the LTE period will include subjects in the safety population for the LTE period, i.e., all randomized subjects who received at least one dose of study treatment in the LTE period. The incidence rate table of adverse events in the placebo-controlled and LTE active treatment period will include subjects in the safety population for the active treatment period, i.e., all randomized subjects who received at least one dose of study treatment in the active treatment period. In this SAP we do not separately define the analysis set in each analysis period.

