5.2.3 Protocol Deviations

Protocol deviations identified during site monitoring will be captured in a Protocol Deviation log and categorized as major or minor deviations based on Protocol Deviation Classification. The major protocol deviations occurred in the LTE period will be summarized for subjects enrolled in LTE. The major protocol deviations for all FAS subjects in the combined placebo-controlled and LTE periods will also be summarized. Major and minor protocol deviations for all FAS subjects will be listed, respectively, across the placebo-controlled period and the LTE period. Subjects who had incorrect dose assigned by interactive response technology (IRT) in LTE will be summarized and listed. This data will be provided by the unblinded monitors. All summaries for protocol deviations will be presented only by LTE treatment group.

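### The safety MRI and ADA evaluable sets are cut from the as-randomised FAS, and the ADA set admits late-start participants with no sample after BIIB092

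*SAP*

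**What the plan says.** **Parent sets (SAP 3.1).** "The Safety MRI Evaluable Set is defined as subjects in the FAS who had at least one post-baseline safety MRI scan". The ADA Evaluable Set is also a subset of the FAS, needing an evaluable post-baseline sample. The FAS is analysed "according to their randomized treatment assignment regardless of treatment received". For the Safety Analysis Set the rule is the opposite: "In analyses performed on the Safety Analysis Set, subjects will be analyzed according to their actual treatment received". The SAP describes its membership as "essentially the same set of participants included in the FAS", so the two sets differ in grouping and not in people.

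**Which set serves which output.** SAP 5.4.1.1 assigns AEs, SAEs, laboratory, C-SSRS, ECG and vital sign data to the Safety Analysis Set, and MRI data to the Safety MRI Evaluable Set. SAP 5.7.1 assigns ADA data to the ADA set.

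**Dosing errors (SAP 5.2.3).** "Subjects who had incorrect dose assigned by interactive response technology (IRT) in LTE will be summarized and listed".

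**Period and baseline.** SAP 5.4.9 and 5.7.1 both report over the placebo-controlled and LTE active treatment period. SAP 3.2 lets set and period jointly decide who enters an output, and then adds: "In this SAP we do not separately define the analysis set in each analysis period". SAP 3.4 gives each period its own baseline. In the active treatment period, a late-start participant's baseline is the last value before the first BIIB092 dose. SAP 5.7.1 overrides this for ADA and takes everyone's baseline before the first dose in the placebo-controlled period.

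**The concern.** Two things look wrong.

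The first is the allocation basis. Within one safety report, most tables place a participant by dose received, while the MRI and ADA tables rest on sets whose only stated parent rule is dose randomised. A reader comparing edema, microhemorrhage or antibody results with the AE profile by dose would assume that the columns hold the same people. After an IRT error they may not.

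The second concerns late-start participants, who had up to 76 weeks of placebo before BIIB092. An evaluable set that asks only for a post-baseline measurement needs a clear statement of which baseline. Without it, measurements taken on placebo could make a participant evaluable for BIIB092. For ADA that would affect the rate in the group newly exposed to 2000 mg. For MRI the same question deserves a check, since the Version 4 amendment summary says: "The Week 104 MRI represents a critical safety assessment for participants switching from placebo to treatment during the LTE".

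**Working it through.** The plan gives no MRI or ADA denominator, event rate or count of dosing errors, so there is no stated figure to reproduce.

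**1. Allocation basis.**
- FAS: as randomised. Safety Analysis Set: as treated. Both are stated in SAP 3.1.
- MRI and ADA sets: subsets of the FAS, with no grouping rule of their own.
- SAP 5.4.1.2 applies the LTE treatment groups to all safety analyses. SAP 3.3 attaches the per-randomisation label only to the efficacy and health outcome groups. These sections name the columns but do not say how a misdosed participant is placed.

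The only written rule that reaches the two sets is therefore the FAS rule.

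**2. Size of one misplaced participant.** Inputs: 654 randomised (Protocol 7.1) and a 1:1:2:2 ratio with the low-dose group split equally between two regimens (Protocol 16.10). I assume that over-enrolment kept the ratio.
- One low-dose regimen: 654 / 12 = 54.5, and 1 / 54.5 = 1.8 percentage points.
- The same at the planned size: 528 / 12 = 44, and 1 / 44 = 2.3 points.
- High-dose column: 654 / 3 = 218, and 1 / 218 = 0.5 points.

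**3. ADA: who qualifies.**
- Samples are taken on Day 1 and at Weeks 4, 24, 48, 76, 80, 104 and later, all before dosing (Protocol 13.6).
- For a late-start participant, the Week 4 to Week 76 samples are on placebo, and the Week 80 sample precedes the first BIIB092 infusion.
- Against the baseline in SAP 5.7.1, all of these are post-baseline. A participant dosed in the LTE but never sampled afterwards therefore meets the set definition.
- SAP Table 10 opens its Week 80 window on the day of the first LTE infusion. The pre-dose Week 80 sample is thus mapped to the LTE, although it reflects no BIIB092.
- Those affected have neither a Week 104 sample nor one at the Follow-up Safety Visit 14 weeks after the last dose, where ADA is also drawn (Protocol Table 4).
- If a share f of the late-start group is in this position and counted negative, a true proportion p is reported as p(1 − f). The documents give neither f nor p. The error can also run the other way: a positive result that arose on placebo is measured against a pre-placebo baseline and may be read as emerging on BIIB092.

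**4. MRI: who qualifies.**
- SAP 3.2 admits only LTE data for late-start participants in this period and removes placebo participants never dosed in the LTE.
- SAP 3.4 puts the late-start baseline at the last value before the first BIIB092 dose. Scans at Weeks 28, 52 and 78 are then at or before baseline.
- Table 16 gives MRI windows on that baseline. With Day 1 = Week 80 = Day 561: Week 104 is 729 − 561 + 1 = 169; Week 156 is 1093 − 561 + 1 = 533; Week 226 is 1583 − 561 + 1 = 1023. The midpoints are (169 + 533) / 2 = 351 and (533 + 1023) / 2 = 778. All match the table.
- The laboratory, ECG and vital sign sections (5.4.3, 5.4.5, 5.4.6) each state which baseline serves early-start and late-start participants. SAP 5.4.9 does not.

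**5. Why a not-assessed count is useful.** Protocol 10.3 says "An MRI scan should be performed if withdrawal occurs" at least 6 months after the previous MRI. From Week 78, Day 547 + 182 = Day 729, which is Week 104. A participant who withdraws between Weeks 80 and 104 may therefore have no scan on drug.

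**The case against.** **A stronger reading is tempting for MRI.** A reader might infer that late-start participants scanned only on placebo enter the BIIB092 denominator as negatives, so that edema, microhemorrhage and siderosis are understated in that group. The documents do not support this. The period rule, the period-specific baseline and Table 16 together make placebo-period scans non-qualifying. SAP 5.1 adds that categorical summaries generally give percentages of those with data. What is missing is an explicit sentence, so no dilution figure for MRI is justified.

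**On grouping**, it is fair to say that the as-randomised rule is written for analyses on the FAS, and that no section expressly says MRI or ADA results are shown by randomised dose. The per-randomisation label is also absent from the safety groups. This makes the as-randomised outcome an inference. It does not supply the opposite rule, and the as-treated rule is attached only to a set that these outputs do not use. Listing IRT errors under 5.2.3 shows who was misdosed but does not align the tables.

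**On ADA**, Table 11 gives windows on an LTE baseline, with Week 80 as baseline and Week 104 first afterwards. That may show what was intended. But the text of 5.7.1 fixes the other baseline, and Table 10 refers its baseline to a Section 3.7.1 that this SAP does not contain. The percentage rule in 5.1 does not remove the problem, because a participant with only a Week 80 pre-dose sample does have data in the LTE window.

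**Conclusion.** The point holds in two limited parts.

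- **Allocation basis.** The MRI and ADA sets inherit an as-randomised parent while the other safety outputs use treatment received. The effect is confined to participants whose received and assigned doses differ. Each is worth about 1.8 points in a low-dose regimen column and about 0.5 in a high-dose column, if the ratio held at 654. The number of such participants is not given.
- **ADA evaluability.** As written, late-start participants with no sample after BIIB092 can be counted, and the Week 80 pre-dose sample is shown as an LTE result. The late-start rate can be diluted or distorted. The proportional dilution equals the unsampled share, which the documents do not give and which attendance at the follow-up visit would reduce.

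For MRI evaluability there is only a wording gap: the intended baseline can be derived but is not stated.

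**What to change.** - In SAP 3.1, define the Safety MRI and ADA Evaluable Sets as members of the Safety Analysis Set, grouped by treatment received under the same rule as the AE tables. For active-treatment-period outputs, require at least one scan or sample after the first BIIB092 infusion.
- In 5.4.9 and 5.7.1, state that the LTE baseline applies to late-start participants and the placebo-controlled baseline to early-start participants. The late-start Week 80 pre-dose ADA sample then becomes baseline, as Table 11 already has it. Correct the section reference in Table 10.
- In both outputs, show the number dosed but not assessed on drug, by group.

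The cost is SAP wording and programming, with no new data. The one downside is a slightly smaller late-start denominator.

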3.2 Analyses Period

Depending on the purpose, different analyses will be conducted on the following study periods:

1. LTE period. Only data in the LTE period will be included in these analyses. This LTE analysis period will be applied to all the AE analyses, and the analyses will include all subjects who were dosed in the LTE period.
2. Placebo-controlled and LTE period. All the data in the placebo-controlled and LTE periods will be included in these analyses. This analysis period will be applied to analyses including, but not limited to all efficacy analyses and listings. The analyses will include all subjects who were dosed in the study including those who did not enroll into the LTE period. For example, line plot of CDR sum of box mean change from baseline over time. in the placebo-controlled and LTE period.
3. Placebo-controlled and LTE active treatment period. Active treatment period is defined as the study period(s) that a subject received BIIB092. For early start subjects – subjects who received BIIB092 in both placebo-controlled and LTE period, all the data (placebo-controlled and LTE periods) will be included in the analyses. For late start subjects – subjects who received placebo in the Placebo-controlled period and BIIB092 in the LTE period, only data in the LTE period will be included. This analysis period will be applied to majority of safety tables, and the analyses will include all subjects who were dosed in the study except for subjects who received only placebo in the placebo-controlled period and did not get dosed in the LTE period. An example is the incidence rate of adverse events in the placebo-controlled and LTE active treatment period.

Subjects to be included in a certain output is determined by both the analysis set and the analysis period. For example, the incidence table of adverse events in the LTE period will include subjects in the safety population for the LTE period, i.e., all randomized subjects who received at least one dose of study treatment in the LTE period. The incidence rate table of adverse events in the placebo-controlled and LTE active treatment period will include subjects in the safety population for the active treatment period, i.e., all randomized subjects who received at least one dose of study treatment in the active treatment period. In this SAP we do not separately define the analysis set in each analysis period.

3.3 Study Treatment

For efficacy and health outcome analyses, the following LTE treatment groups of BIIB092 (per randomization) will be evaluated:

- low-dose (BIIB092 -125mg once every 4weeks or 375mg once every 12weeks)

CONFIDENTIAL

The information contained herein may not be used, disclosed, or published without the written consent of Biogen MA Inc.

	Statistical Analysis Plan Long-Term Extension Period	V1.0
---	---	-------------

- medium-dose (BIIB092 - 600mg once every 4 weeks)
- early start high-dose (BIIB092 - 2000mg once every 4 weeks)
- late start high-dose (BIIB092 - 2000mg once every 4 weeks)

For other analyses, such as safety, PK, PD, biomarker, and anti-drug antibody analyses, low dose group will be split out for different frequencies. The following LTE treatment groups of BIIB092 will be evaluated:

- low-dose 125mg once every 4weeks
- low-dose 375mg once every 12weeks
- medium-dose (BIIB092 - 600mg once every 4 weeks)
- early start high-dose (BIIB092 - 2000mg once every 4 weeks)
- late start high-dose (BIIB092 - 2000mg once every 4 weeks)

Since subjects in low-dose group and medium-dose group are taking the same treatment from the start of placebo-controlled period to the end of LTE period, so the subjects in these treatment groups are all considered as early start subjects. Late start subjects refer to subjects who were on placebo during placebo-controlled period then switched to high-dose (BIIB092 - 2000mg once every 4 weeks). Throughout this SAP, these study treatment schemes will be referred as LTE treatment.

3.4 Dates and Points of Reference

The study day and baseline are defined for each analyses period respectively

1. LTE period

- Study Day 1: the date of the first dose of study treatment in the LTE period
- Study Day
 - For a date on or after Study Day 1

$$\text{Study Day} = (\text{Date of Interest}) - (\text{Study Day 1}) + 1$$
 - For a date before Study Day 1

$$\text{Study Day} = (\text{Date of Interest}) - (\text{Study Day 1})$$
- LTE baseline: the baseline value for the LTE period is defined as the most recent non-missing measurement collected prior to the first dose in the LTE period.
- Change from baseline will be defined as post-baseline value minus baseline value

2. Placebo-controlled and LTE period

- Study Day 1: the date of the first dose of study treatment in the PC period

CONFIDENTIAL

The information contained herein may not be used, disclosed, or published without the written consent of Biogen MA Inc.

- Study Day
 - For a date on or after Study Day 1
Study Day = (Date of Interest) – (Study Day 1) + 1
 - For a date before Study Day 1
Study Day = (Date of Interest) – (Study Day 1)
- PC and LTE baseline: the baseline value for the Placebo-controlled and LTE period is defined as the most recent non-missing measurement collected prior to the first dose in the PC period.
- Change from baseline will be defined as post-baseline value minus baseline value

3. Placebo-controlled and LTE active treatment period

- Study Day 1: the date of the first dose of BIIB092. For low-dose, medium-dose and early start high-dose subjects, this will be the date of first dose of BIIB092 in the placebo-controlled (PC) period; for late start high-dose subjects, this will be the date of first dose of BIIB092 in the LTE period.
- Study Day
 - For a date on or after Study Day 1
Study Day = (Date of Interest) – (Study Day 1) + 1
 - For a date before Study Day 1
Study Day = (Date of Interest) – (Study Day 1)
- Active treatment baseline: the baseline value for the active treatment period and is defined as the most recent non-missing measurement collected prior to study day 1.
- Change from baseline will be defined as post-baseline value minus baseline value

For data that are summarized by visit, assessment from all scheduled visits, EOS visit and unscheduled visits will be mapped to an appropriate analysis visit using a windowing scheme as describe in [Appendix I](#)

